7.7 MRI and Laboratory evaluations following Third TACE Cycle

MRIs of the liver, chest and pelvis and laboratory evaluations must be done within 4 weeks (± 1 week) of the third TACE cycle. If the patient received treatment for bilobar disease, the MRIs and laboratory tests must be done within 4 weeks (± 1 week) of the embolization of the second lobe.

Laboratory evaluations will include those listed under screening, at a minimum, and results will be reviewed by the investigator and clinically significant changes from baseline will be reported as adverse events. MRI results of the liver will be reviewed by Central Reviewers. If the patient has experienced a cardiac related adverse event, cardiac ejection fraction testing will be done using the same method as at screening.

7.8 Post Final Study TACE Cycle visit (within 4 weeks +/- 1 week after final study MRI)

After the patient has had his/her final TACE cycle, MRI and laboratory evaluations according to the schedule above, patient will have a final study visit within 4 weeks (± 1 week) after the final study MRI. The treatment schedule for this study ends after the following evaluations.

- Physical exam, including vital signs and weight
- Recording of concomitant medications
- ECG
- Urinalysis (Specific Gravity, Protein, Glucose, Blood)
- ECOG performance status evaluation
- Cardiac ejection fraction testing using the same method as at screening
- Adverse event assessment
- Laboratory tests
 - CBC (RBC, WBC, Platelet Count, Hemoglobin, Hematocrit, ANC)
 - AST
 - ALT
 - AFP
 - Total Bilirubin
 - Albumin
 - aPTT/PT/INR
 - Alkaline phosphatase
 - Serum creatinine

7.9 Survival follow -up

Patients will be followed from date of first embolization of the first cycle until a date of death is obtained or the patient is lost to follow up. Survival contacts will be attempted every 3 months after completion of final protocol-specified study visit. Contacts may be by visit, telephone, email, or written response, and may be obtained from the patient, medical records, or care givers/family members. Patients may undergo further treatment after the study-specified TACE treatments at the discretion of their physicians, including but not limited to transplant, resection, percutaneous ethanol injection (PEI), radiofrequency ablation (RFA), additional

embolizations, sorafenib or other treatments, including other investigational methods. Patients who have additional embolizations after the three protocol-defined TACE cycles must have the same type of embolization (cTACE or hqTACE) they received during the study. It would be unethical to deny these patients further treatment which might provide benefit, but any and all of the above could affect long term survival and be confounds in the analysis and interpretation of this study data. For this reason treatments and outcomes after the final study TACE will be documented, to the extent possible, during the survival follow-up period, but will not be considered safety or efficacy outcomes in this study, except time to untreatable progression (TTUP). Survival and TTUP will be the only outcomes evaluated after completion of the protocol specified treatment phase of the investigation.

7. Withdrawal of Patients

Patients will be informed that they have the right to withdraw from the study at any time for any reason, without prejudice to their medical care. The investigator also has the right to withdraw patients from the study for any of the following reasons:

- Adverse events, including cardiac ejection fraction <50%
- Progression to extrahepatic disease
- Refusal of treatment
- Patient request
- Inability to complete study procedures
- Lost to follow up
- Non compliance with study requirements

If a patient is withdrawn or discontinued from the study, the reason for withdrawal from the study will be recorded in the source documents and on the Study Termination CRF. All patients withdrawn from the study should be encouraged to complete, if possible, all clinical evaluations scheduled for the final visit. All adverse events should be followed as described in Section 9. The patient will be asked to give consent for survival follow-up contacts to be performed. Patients who are withdrawn from the study for any reason will not be replaced.

The study may be discontinued if, in the opinion of the Sponsor and/or the Data Safety Monitoring Board (DSMB), there is a significant risk to patients as evidenced by higher than anticipated adverse event rates, concern regarding unexpected serious adverse events, or device failures resulting in adverse events.

8. Adverse Events

9.1 Non-serious Adverse Events

9.1.1 Assessments

The Investigators are responsible for monitoring the safety of patients who have been randomized in this study. All AEs considered to be related to study treatment, including doxorubicin treatment, will be followed until the event resolves. If patients receive other

anticancer therapy the follow-up for AEs will be stopped. AEs will be evaluated for severity using NCI CTCAE (Common Toxicity Criteria for Adverse Events), where applicable.

Investigators are required to document all AEs occurring during the study commencing with the date of randomization and including the protocol defined post-treatment follow-up period (21 CFR §312.64[b]), which is defined as 30 days post last MRI in this study, on the designated CRF pages. It is also important to record all AEs that result in permanent discontinuation of the study treatment, whether serious or non-serious. AEs that occur following the signature of informed consent but prior to randomization will not be captured. AEs that occur after the patient receives any anticancer therapy other than the study treatment they were randomized to receive will not be recorded as AEs.

Serious adverse events (SAEs), as defined below, must be reported to BioSphere Medical or its representative within 24 hours of knowledge of their first occurrence. SAEs that occur following the signature of the informed consent but prior to the first TACE procedure will not be reported. SAEs that occur after patients receive any anticancer therapy other than the study treatment they were randomized to will not be reported.

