11.6.6 Electrocardiogram (ECG)

Electrocardiograms will be performed at baseline and the final study visit. Investigators will interpret the results and classify each ECG as follows:

- Normal
- Abnormal, not clinically significant
- Abnormal, clinically significant

For all abnormal findings, the investigator will provide a brief description of the abnormality. All clinically significant abnormal findings found at the final study visit which were not present at baseline will be reported as adverse events. A summary table will be generated summarizing the ECG results for baseline and final study visit as classified by the PI as the number and percent of patients in each category for each treatment group. All ECG data will be reported in the data listings.

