11.6.7 Cardiac Ejection Fraction (%)

Cardiac ejection fraction data will be collected at screening, after the second TACE, and at the final study visit for all patients. Cardiac ejection fraction testing will also be collected at additional time points during the protocol specified treatment phase of the investigation if the patient has experienced a cardiac related adverse event. Abnormal findings will be reported as adverse events. A summary table will be created summarizing the number and percent of patients having a clinically significant cardiac ejection fraction finding at each time point for each treatment group. This data will be presented in the data listings.

12 Data Safety Monitoring Board

A Data Safety Monitoring Board will be formed consisting of at least 3 individuals with expertise and experience in clinical trials, liver cancer and safety evaluations, but without direct involvement in the conduct of the study. The exact responsibilities, procedures, and guidelines used to manage the DSMB are described in a separate charter.

13 Records and Confidentiality

Each patient will be identified by study number only in the trial records. Study data will be recorded on pre-printed CRFs. Monitoring of study data recorded on the CRFs to source documents will be conducted for all patients to ensure accuracy and completeness.

14 Quality Control and Assurance

This study will be initiated and conducted under the sponsorship of BioSphere Medical, Inc., a wholly owned subsidiary of Merit Medical Inc. BioSphere Medical will supply pre-printed CRFs to all sites. Representatives of BioSphere Medical will monitor the study to verify study data, medical records, and CRF data in accordance with current ICH, GCPs and other applicable regulations and guidelines.

15 Good Clinical Practice

The study will be conducted in accordance with the International Conference on Harmonization (ICH) E6 for Good Clinical Practice (GCP): Consolidated Guidance and the appropriate regulatory requirement(s). The investigators will be thoroughly familiar with the appropriate use of the treatment procedure as described in the protocol. Essential clinical documents will be maintained to demonstrate the validity of the study and the integrity of the data collected. Master files should be established at the beginning of the study, maintained for the duration of the trial and retained according to the appropriate regulations.

16 Ethical Considerations

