APPENDIX A

1. Study Flowchart: Unilobar Disease

[figure not shown]
2. Study Flowchart: Bilobar Disease

3. Schedule of Study Events

1. Study Flowchart: Patients with Unilobar Disease

2. Study Flowchart: Patients with Bilobar Disease

3. Schedule of Procedures						
	Screening (within 4 weeks +/- 1 week of first TACE)	TACE Treatment Period ¹			Post-final TACE Study Visit ²	Survival Follow- up ³
	Visit -1	Tx Visit 1	Tx Visit 2	Tx Visit 3	Visit 4	
Informed Consent	X					
Eligibility criteria assessment	X					
Demographics	X					
Baseline HCC Review ⁴	X					
Medical History	X					
Concurrent Medical Conditions	X					
Physical Examination ⁵	X				X	
Vital signs	X				X	
Serum Pregnancy test	X					
Hematology / Serum Chemistry ⁶	X	X	X	X	X	
Urinalysis	X	X	X	X	X	
Tumor Evaluations (MRI) ⁶	X	X	X	X		
Alpha-feto protein (AFP) ⁶	X	X	X	X	X	
12-lead ECG	X				X	
Cardiac Ejection Fraction ⁷	X		X		X	
Randomization ⁸						
Embolization procedures (TACE)		X	X	X		
Resource Utilization		X	X	X		
Adverse Events		From randomization to protocol defined follow- up period				
Concomitant Medications		X				
Protocol deviations/violations		X				
Survival status						X
Additional cancer treatments						X
Pharmacokinetic Sampling ⁹		X				

¹ First TACE Cycle must be begin within 4 weeks (± 1 week) of baseline MRI and labs. If the patient has bilobar disease, the embolization of the first lobe must be within 4 weeks (± 1 week) of baseline MRI and labs and the second lobe must undergo embolization within 4 weeks (± 1 week) of the first lobe.

A second TACE cycle is required for all patients, unless the investigator deems further treatment unsafe for the patient. The second TACE cycle must be within 8 weeks (± 2 weeks) of first TACE cycle. If the patient has bilobar disease, the first lobe of the second TACE cycle must undergo chemoembolization within 8 weeks (± 2 weeks) of the second lobe in the first TACE cycle, and the second lobe of the second TACE cycle must undergo chemoembolization within 4 weeks (± 1 week) of first lobe in the second TACE cycle.

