A third TACE cycle will be done for patients with MRI results for the liver after the second TACE cycle that demonstrate less than complete necrosis, as interpreted by the Central Reviewers, according to mRECIST criteria. The third TACE cycle must be done within 8 weeks (± 2 weeks) of the second TACE cycle. If the patient has bilobar disease, the first lobe of the third TACE cycle must undergo chemoembolization within 8 weeks (± 2 weeks) of the second lobe of the second TACE cycle, and the second lobe of the third TACE cycle must undergo chemoembolization within 4 weeks (± 1 week) of the first lobe in the third TACE cycle.

² Post final TACE study visit must occur within 4 weeks (± 1 week) of the final study MRI.

³ Patients will be followed for survival for 2 years after the first TACE embolization. Survival contacts will be performed every 3 months.

⁴ Includes baseline disease status (Child Pugh, Unilobar/Bilobar status, ECOG), prior hepatic treatments, risk factor assessment, and assessment for relevant baseline medical conditions.

⁵ Physical exam for the Post final TACE visit must be within 4 weeks (± 1 week) of final study MRI.

⁶ MRIs and labs (including AFP) will be performed 4 weeks (± 1 week) after each TACE cycle. For patients with bilobar disease, MRI must be within 4 weeks (± 1 week) of the second lobe embolization.

⁷ Cardiac ejection fraction may also be assessed as clinically indicated to evaluate a cardiac adverse event.

⁸ Randomization will occur as close to the day of the scheduled First TACE procedure as possible, preferably on the same day.

⁹ A blood sample will be drawn for PK analysis between 6a and 8a the day after the first embolization of the first TACE Cycle, again 6-8 hours later for patients who have not been discharged at that time, and on the day of the first follow-up MRI.

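### Adverse event collection is timed from the last MRI, so read literally it can close up to 5 days before the final safety visit and, where the last embolization has no later MRI, around or before that embolization

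*Combined protocol and SAP*

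**What the plan says.** Section 9.1.1 asks investigators to document AEs from randomization through a post-treatment follow-up period, "which is defined as 30 days post last MRI in this study". The AE row of the Schedule of Procedures (Appendix A) points to the same end: "From randomization to protocol defined follow- up period".

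The final visit has a different limit. Under Section 7.8 the "patient will have a final study visit within 4 weeks (± 1 week) after the final study MRI", and its list of evaluations includes "Adverse event assessment", an ECG, ejection fraction and laboratory tests. Two analysis sections then make findings at that visit AEs. Section 11.6.6 says of the ECG: "All clinically significant abnormal findings found at the final study visit which were not present at baseline will be reported as adverse events". Section 11.6.7 says of ejection fraction: "Abnormal findings will be reported as adverse events".

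On imaging, the Appendix A footnotes say "MRIs and labs (including AFP) will be performed 4 weeks (± 1 week) after each TACE cycle". Withdrawn patients "should be encouraged to complete, if possible, all clinical evaluations scheduled for the final visit" (Withdrawal of Patients), and that list of evaluations contains no MRI. Section 11.3.1 keeps every randomized patient with at least one TACE procedure in the Safety Population.

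**The concern.** The end of AE collection depends on a scan, not on the last exposure or the last visit. Two problems follow.

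- **Patients who finish as planned.** The final visit may lawfully take place after collection has closed. For a patient given three cycles, it also carries the only routine ejection fraction test after the last doxorubicin exposure: the scheduled test before it follows cycle 2, and after cycle 3 a test is done only if a cardiac AE has occurred. Decline in ejection fraction is the first doxorubicin-related AE listed in Section 11.6.1.
- **Patients embolized without a later MRI.** Their last MRI precedes their last exposure, so the 30 days are partly or wholly used up before that embolization. They stay in the safety denominator with little or no required collection after it. The plan foresees such patients for efficacy (Section 11.5.2 counts those who discontinue before a post-baseline evaluation as progressed, and Section 11.5.6 gives those with no post-baseline MRI a censoring date), but the AE rule makes no matching provision.

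Overall and doxorubicin-related AE rates are secondary objectives, so uneven capture would affect named comparisons.

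**Working it through.** **Inputs (protocol windows)**

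- End of AE collection: last MRI + 30 days (9.1.1).
- Final visit: 4 ± 1 weeks after the final MRI, days 21 to 35 (7.8).
- MRI after a cycle: 3 to 5 weeks, nominal 4 (7.3, 7.5, 7.7).
- Next cycle: 6 to 10 weeks after the previous one, nominal 8 (7.4, 7.6).
- Second lobe: 3 to 5 weeks after the first, nominal 4 (7.2, 7.4, 7.6).
- Baseline MRI to first embolization: nominal 4 weeks, at most 5 (7.2).

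**Check that the windows are read as the protocol reads them.** The Treatment and Assessment section puts the response assessment at 15-25 weeks (unilobar) and 24-40 weeks (bilobar).

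- Unilobar: (6 to 10) + (6 to 10) + (3 to 5) = 15 to 25 weeks.
- Bilobar: (3 to 5) + (6 to 10) + (3 to 5) + (6 to 10) + (3 to 5) + (3 to 5) = 24 to 40 weeks.

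Both figures are reproduced exactly.

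**Final visit against cutoff** (visit day − 30)

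- Earliest: 21 − 30 = −9. Nominal: 28 − 30 = −2. Latest: 35 − 30 = +5.
- The cutoff precedes the visit only for visits on days 31 to 35, by at most 5 days.

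**Cutoff relative to the last embolization.** Formula: 30 − (days from last MRI to last embolization). Positive means the cutoff falls after the embolization, negative before it.

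| Last embolization has no later MRI | Nominal | Range |
|---|---|---|
| Cycle 2 or 3, unilobar or first lobe | 30 − 7×(8−4) = +2 | 30 − 7×(6−5) = +23 to 30 − 7×(10−3) = −19 |
| Cycle 2 or 3, bilobar second lobe | 30 − 7×(8−4+4) = −26 | 30 − 7×(6−5+3) = +2 to 30 − 7×(10−3+5) = −54 |
| Cycle 1, baseline MRI only, unilobar or first lobe | 30 − 28 = +2 | +9 to −5 if the MRI was 3 to 5 weeks earlier; up to +30 if same day |
| Cycle 1, baseline MRI only, second lobe | 30 − 7×(4+4) = −26 | +9 (baseline MRI same day as the first lobe) to 30 − 7×(5+5) = −40 |

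**Comparison: the last cycle's MRI is done on schedule.** Collection after the last embolization runs 7×3 + 30 = 51 to 7×5 + 30 = 65 days, nominal 58. The second problem is therefore confined to patients who lack that MRI.

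**The case against.** The strongest reply is that the 30-day clause was never meant as a cap. Section 9.1.1 asks for all AEs during the study and adds the follow-up period to that; a post-treatment period that ends before treatment makes no sense. Section 9.1.2 has AEs assessed at every visit. Section 11.6.1 sets no MRI-based end for treatment-emergent events and compares arms over the treatment phase, which runs through the follow-up procedures. On that view a site would simply record what it finds. This has force, but it shows that the passages conflict rather than that the conflict is resolved. The explicit definition and the schedule row point the other way, and sites may differ in which they follow.

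Three stronger readings are tempting, and the documents do not support them.

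- **That the events which made patients stop are lost.** Section 9.1.1 separately requires AEs leading to permanent discontinuation to be recorded, serious or not, without a time limit. Section 9.2.2 requires serious and unanticipated events during the investigation to be reported. Treatment-related events are followed to resolution, although that covers events already recorded and not new ones.
- **That stopping treatment means a short window.** The MRI is required after each cycle, and the rule allowing an investigator to withhold the next cycle does not waive it. Some patients without a later MRI will have died, been lost or moved to other anticancer therapy, where AE recording ends anyway; a longer window recovers little from them.
- **That the arm comparison is biased.** The background reports 20 versus 4 grade 3 or 4 events in a 30-patient study. Those are event counts and say nothing about early stopping or missed MRIs by arm.

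Likewise, days 31 to 35 are 5 of the 15 permitted visit days, which is not a share of patients, and an abnormality found on day 33 may have begun before day 30.

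**Conclusion.** The point holds in a limited form. The stated end of AE collection conflicts with the plan's own final visit, by at most 5 days and not at all at nominal timing. For patients whose last embolization has no later MRI, the literal cutoff lies nominally 2 days after it, or 26 days before it for a bilobar second lobe, against 51 to 65 days for other patients. What could be missed is mainly new, later, non-serious events of anticipated types. Section 9.1.2 lists alopecia, mucositis, skin discoloration and myelosuppression as anticipated, so the doxorubicin comparison is within reach.

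This rests on reading the 30-day definition literally and on the visit windows above. Reading the final-visit window as 0 to 5 weeks leaves the latest day at 35, so the first part is unchanged. The number of patients without a later MRI is not given. For scale only, each 1% of the 510 planned (2 × 255) would be about 5 patients. The size and direction of any effect on the comparison between arms are unknown. The primary survival analysis is not touched.

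**What to change.** In Section 9.1.1, define the end of AE collection as the latest of:

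- the Section 7.8 final visit;
- 30 days after the last study MRI;
- a fixed period after the last study embolization, with the length set by the sponsor (for example at least 30 days).

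Keep the existing stop when a patient starts other anticancer therapy. Apply the rule to withdrawn patients who still consent to contact, by telephone if they do not attend. Use the same end date for treatment-emergent AEs in Section 11.6.1 and in the AE row of the Schedule of Procedures.

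With a 30-day period, the gap before the final visit becomes 0 days, and every patient who can be contacted and has not started other therapy has at least 30 days of collection after the last exposure. Patients with the last cycle's MRI keep their 51 to 65 days. The cost is one sentence with matching wording in two places, a few telephone contacts and slightly higher AE counts. No treatment and no primary analysis changes.

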9.1.2 Definitions

An AE is any untoward medical occurrence in a patient or clinical investigation patient and does not necessarily have to have a causal relationship with the treatment. An AE therefore can be any unfavorable or unintended sign (including an abnormal laboratory finding, for example), symptom or disease temporally associated with the use of a medicinal product or procedure, whether or not considered related to the product or procedure. A non-serious AE is any untoward medical occurrence that does not meet any of the criteria for an SAE as defined below.

Anticipated adverse events are those which typically occur due to embolization (pain, fever, fatigue, nausea, elevated liver enzymes, infection, abscess, cholecystitis, hemorrhage, thromboembolism, etc), or are drug related (alopecia, nausea, mucositis, rash, skin discoloration, myelosuppression, changes in cardiac function, etc), or are related to liver disease progression (jaundice, new tumors, biliary obstruction, metastasis, liver failure, death), or relate to pre-existing conditions. Unanticipated events are those not typically seen as a result of chemoembolization. Unanticipated adverse events must be reported to the sponsor within 24 hours of site notification of the event.

Laboratory data are to be collected as stipulated in this protocol. Clinical syndromes associated with laboratory abnormalities are to be recorded as appropriate (eg, diabetes mellitus instead of hyperglycemia).

Progression of hepatocellular carcinoma is considered an efficacy outcome parameter and should not be captured as an AE.

Patients should be instructed to report any AE that they experience to the Investigator or Study Coordinator. Patients will be assessed for AEs at each visit. AEs occurring during the clinical trial and the protocol-defined follow-up period should be recorded on the appropriate AE CRF. In order to capture the most potentially relevant safety information during this study, it is important that the Investigators record AE terms accurately and consistently throughout the study. Wherever possible, a specific disease or syndrome should be reported on the CRF rather than the associated individual signs and symptoms. If observed or reported signs or symptoms are not considered a component of a specific disease or syndrome by the Investigator, they should be recorded as separate AEs on the CRF.

